This is a multicenter observational study to develop predictive models for sepsis and necrotizing enterocolitis in preterm infants, using clinical, laboratory, and bedside monitor data.

- No interventions are involved.
- Clinical, laboratory, and imaging data will be collected from the medical record.
- Vital sign data will be collected from the bedside monitors.
- Machine learning will be used to develop, test, and validate predictive algorithms

SYNOPSIS

Title: Predictive Modeling for sepsis and necrotizing enterocolitis in preterm infants
Investigators: [name].; [name].
Planned Study Initiation: November 2018
Study Duration: 10 years
Length of subject participation: Study data are collected from birth until NICU discharge. Neurodevelopmental follow-up data will be collected until age 2.
Objective: To test the hypothesis that validated algorithms combining cardiorespiratory metrics from NICU bedside monitors with clinical, demographic and laboratory variables can provide early warning for sepsis and NEC in VLBW infants in the NICU.
Outcomes: Primary: 
• Late-onset (>3d of age) sepsis• Other late-onset infections• Necrotizing enterocolitis Secondary: 
• Mortality• Days on mechanical ventilation• Preterm morbidities including but not limited to brain injury, retinopathy, acute kidney injury, and bronchopulmonary dysplasia• Days on antibiotics• Length of NICU stay• Neurodevelopmental outcomes at routine NICU follow-up visits

IRB # 21237: Predictive Modeling for Sepsis and Necrotizing Enterocolitis in Preterm Infants

NICHD: RO1 HD072071:

PI: [name],

Version dated March 10, 2025

Methodology: Observational study with data collection from electronic health record
Total Number of infants planned: 8500
Inclusion criteria:

 • Birthweight <1500 grams
Exclusion criteria:

 • None
Investigational intervention: None (data collection only)
Other study intervention(s): None
Statistical methods: Descriptive statistics, logistic regression, decision tree, neural network, deep learning and others will be utilized.
Efficacy: Algorithms for sepsis and NEC risk will be developed and externally validated and cross-validated.
Safety: Patient data will be linked and coded within sites (with PHI stored on research drives behind fire walls). Only data with limited HIPAA identifiers (dates and study IDs but no key to the code) will be shared between sites.

LIST OF ABBREVIATIONS

Abbreviation or specialist term	Explanation
BPD	Bronchopulmonary Dysplasia
CBC/Diff	Complete Blood Count and differential
Corrected Age	Chronologic age in months, minus #months premature (used after NICU discharge)
CRC	Clinical Research Coordinator
CRF	Case Report Form
CRP	C Reactive Protein
GA	Gestational Age
HUS	Head ultrasound
IRB	Institutional Review Board
IVH	Intraventricular Hemorrhage
MOP	Manual of Procedures
NEC	Necrotizing Enterocolitis
NICU	Neonatal Intensive Care Unit
PMA	Postmenstrual age (gestational age plus chronologic age in weeks, used during NICU
cPVL	Cystic Periventricular Leukomalacia

IRB # 21237: Predictive Modeling for Sepsis and Necrotizing Enterocolitis in Preterm Infants

NICHD: RO1 HD072071:

PI: [name],

Version dated March 10, 2025

REDCap	Research Electronic Data Capture
ROP	Retinopathy of Prematurity
UVA	University of Virginia
VLBW	Very Low Birth Weight (<1500 grams)

[Table of Contents](#)

1	BACKGROUND AND RATIONALE	Error! Bookmark not defined.
2	STUDY OBJECTIVES.....	3
3	SUBJECT ELIGIBILITY	4
4	STUDY PLAN	5
5	STATISTICAL CONSIDERATIONS	6
6	STUDY MANAGEMENT	7
7	REFERENCES.....	8

IRB # 21237: Predictive Modeling for Sepsis and Necrotizing Enterocolitis in Preterm Infants

NICHD: RO1 HD072071:

PI: [name],

Version dated March 10, 2025

1. BACKGROUND AND RATIONALE

Study Synopsis

In a multi-NICU study, we are developing, testing, and validating predictive modeling algorithms for early detection of sepsis and NEC in VLBW infants.

Disease Background

The number of very low birthweight (VLBW, <1500 g) infants born in the US each year remains about 60,000(1). Their course of post-natal development in the NICU centers on support of ventilation and nutrition while systems mature. There are, however, interruptions by the apparently sudden onset of inflammatory illnesses such as sepsis and necrotizing enterocolitis (NEC), occurring in approximately 15% and 8% of VLBW infants, respectively. The mortality is high and there is substantial short- and long-term morbidity(2)(3)(4). These illnesses are not really sudden, though – clinical signs of illness occur relatively late, when the systemic inflammatory response is well-developed. Effective detection systems would allow earlier recognition and treatment.

Many have postulated that new analysis of existing data from standard-of-care bedside monitors should give clues that are useful in early diagnosis(5)(6)(7). The University of Virginia group has reduced one such analysis to clinical practice. We found abnormal heart rate characteristics (HRC) of reduced variability and transient decelerations in the heart rates of septic infants for 12 to 24 hours and more prior to clinical suspicion(8). We developed mathematical tools to detect abnormal HRC, validated them externally, demonstrated their relationship to clinical data such as lab results and other findings, and performed a large randomized trial to assess impact on VLBW outcome(9). The results were important – a more than 20% mortality reduction when HRC monitors were displayed to clinicians with no other intervention mandated. Since then we have shown that adding other vital sign data, such as oxygen saturation, as well as other demographic and clinical data, including laboratory values, might improve on heart rate characteristics monitoring for predicting sepsis, NEC, and other outcomes(10)(11).

Rationale for Study Design

- Routinely monitored cardiorespiratory signals hold much physiologic information that is not synthesized in such a way as to alert clinicians to subtle changes that occur very early in the systemic inflammatory response.
- The combined efforts of clinicians, mathematicians and engineers can lead to effective new monitoring strategies that allow early diagnosis of otherwise invisible clinical deterioration.
- Adding clinical, demographic, and laboratory data to bedside monitor cardiorespiratory data will improve prediction and early detection of sepsis and NEC over any of these data alone.
- Improved analytics will favorably impact patient outcomes by assisting clinicians in decisions about initiation of antibiotics and other therapies early in the course of illness.

IRB # 21237: Predictive Modeling for Sepsis and Necrotizing Enterocolitis in Preterm Infants

NICHD: RO1 HD072071:

PI: [name],

Version dated March 10, 2025

2. STUDY OBJECTIVES

2.1 Hypothesis

Validated algorithms combining bedside monitor cardiorespiratory-based metrics along with clinical, demographic and laboratory variables can provide early warning for sepsis and NEC in VLBW infants in the NICU.

2.2 Specific Aims

- For all VLBW infants, collect baseline demographic and clinical data.
- Characterize, categorize, and catalogue events of sepsis and NEC, and associated clinical and laboratory variables, as well as ventilator status at the time of illness
- Identify metrics of heart rate, respiratory rate, and combined cardiorespiratory characteristics that change in the preclinical phase of sepsis and NEC
- Develop new or optimally adapted mathematical measures that report on abnormal waveforms in the ECG, chest impedance, and/or pulse oximetry signals
- Construct predictive models to predict or detect sepsis or NEC, combining clinical, laboratory, and physiologic monitoring data using standard techniques such as (but not limited to) logistic regression, and using novel approaches from the field of Big Data analytics such as deep neural networks
- Develop and externally validate algorithms on VLBW infants at the other participating NICUs over the course of the study.

3. SUBJECT ELIGIBILITY

Inclusion Criteria

- Birthweight <1500 grams

Exclusion Criteria

- None

4. Study Plan

Clinical Data Collection

REDCap will be used by all sites for electronic data entry. All data required for this study should be documented in the infant's medical record as part of routine care. Data entry guidelines are specified in the Manual of Procedures (MOP). Both retrospective and prospective data will be collected and analyzed.

IRB # 21237: Predictive Modeling for Sepsis and Necrotizing Enterocolitis in Preterm Infants

NICHD: RO1 HD072071:

PI: [name],

Version dated March 10, 2025

Bedside Monitor Data Collection

At all sites, digital waveforms (3 EKG leads, chest impedance, and the O2 saturation) along with q2sec vital signs are stored using BedMasterEx software (Excel Medical), Philips Data Warehouse Connect, or other similar data storage systems. These data are labeled by bed number and a coded timestamp. Retrospective and prospective data will be used for this study.

Clinical data and bedside monitor data will also be collected and shared between sites via UVA Box.

5. STATISTICAL CONSIDERATIONS

Statistical Methods

Clinical, demographic, and cardiorespiratory parameters are combined using multivariate statistical methods, such as logistic regression, k nearest neighbor analysis, random forests, neural nets, and other techniques(12)(13). The period of interest is the 24 hours prior to the event. Thus the output of the model is the probability of an event in the next day. We divide by the average probability of the event, and present the clinician with the fold-increase in risk of an upcoming event. We will have a development/test cohort and validation cohort both within and between centers to account for differences in clinical practices that may impact vital sign patterns.

Study Size Considerations

We anticipate enrolling at least 1667 VLBW infants per site over a 4-year period. With incidence of late-onset sepsis and NEC being approximately 15% and 7% respectively, we anticipate having about 200 episodes of culture-positive sepsis and 100 episodes of NEC with bedside monitor data available for analysis. Generally, 50 events allow for a predictive model with 5 predictive variables and (based on our experience with bootstrapping) 95% CI of 0.3 around the ROC area, so we will have sufficient numbers of infants with events to develop and validate models.

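### Do the plan's statements about laboratory data clash so that their early-warning value goes untested?

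*Combined protocol and SAP*

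**What the plan says.** Section 5 (Statistical Methods) combines clinical, demographic and cardiorespiratory parameters. It fixes the window ("The period of interest is the 24 hours prior to the event") and makes the output a next-day event probability, scaled by the average probability and shown to clinicians as a fold-increase in risk. The word laboratory does not appear in that list.

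Elsewhere laboratory data are clearly intended. The Synopsis objective, the design rationale in Section 1 and the hypothesis in Section 2.1 all include them. The modelling aim in Section 2.2 builds models "combining clinical, laboratory, and physiologic monitoring data".

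Two other aims in Section 2.2 concern data collection. The first reads "For all VLBW infants, collect baseline demographic and clinical data". The second is to characterise, categorise and "catalogue events of sepsis and NEC, and associated clinical and laboratory variables, as well as ventilator status at the time of illness".

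The Synopsis says that laboratory data are taken from the medical record and that study data run from birth to discharge from the unit. Section 4 says the required data should already be in the record through routine care, and leaves data-entry rules to a Manual of Procedures that was not supplied.

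**The concern.** On a quick reading, three statements pull apart. The hypothesis needs laboratory predictors, the only statistical section does not list them, and the aim that mentions how they are gathered attaches them to episodes of illness.

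If laboratory values existed only for events, a complete-case model would have no comparison periods. Filling in the missing values would separate events from non-events by how they were recorded.

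If the values came from recognised illness, they would describe a stage that Section 1 itself regards as late: "clinical signs of illness occur relatively late, when the systemic inflammatory response is well-developed". A model trained on them might look strong and then do poorly in the period that matters for early warning. Because the output is to be shown to clinicians, that would be a real fault.

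**Working it through.** No figure in the plan bears directly on this point, so the check is mainly a comparison of the text.

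**1. Are laboratory data left out of the model?** Section 1, in describing the group's earlier work, twice presents laboratory results as an example of clinical data. Section 4 has only two data streams, clinical and bedside monitor, and laboratory results can belong only to the first. On that usage the clinical parameters in Section 5 include laboratory values. The modelling aim names them outright. The Synopsis, the rationale, the hypothesis and that aim list laboratory data separately from clinical data, so usage is inconsistent, but nothing excludes them.

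**2. Does the second aim set a predictor rule?** Its verbs are descriptive. It does not say that the catalogued values enter a model, and the reference to the time of illness may attach to ventilator status alone. Describing an episode when it occurs and modelling the preceding 24 hours can both be done. Section 5 makes no exception to its window for any type of predictor.

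**3. Are laboratory values collected only for events?** The second aim contains no such restriction, and the Synopsis places none on infants or times. The planned output also argues against it: a next-day probability, divided by an average probability, cannot be estimated without event-free time. Reading the restriction in would make the plan's own laboratory model impossible to fit.

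**4. How many infants would be affected if it were read in?** Inputs: 8,500 planned infants (Synopsis) and, for sepsis and NEC, "occurring in approximately 15% and 8% of VLBW infants, respectively" (Section 1; Section 5 gives 7% for NEC).

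- No infant has both: 1 − 0.15 − 0.08 = 0.77, and 8,500 × 0.77 = 6,545. With 7% NEC the share is 0.78.
- Every NEC infant also has sepsis: 1 − 0.15 = 0.85, and 8,500 × 0.85 = 7,225.

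These are expected numbers with neither illness. They become numbers without laboratory data only under the restriction rejected in step 3.

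**5. Can the effect on ROC area be sized?** Only with assumed inputs. Take a monitor-only area of 0.70, so d = √2 × Φ⁻¹(0.70) = 0.742 SD. Add an independent laboratory value shifted by D at illness, with a fraction f of that shift already present beforehand, and fit the weights on at-illness values.

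- Area with at-illness values: Φ(√(d² + D²)/√2).
- Same model used before illness: Φ((d² + fD²)/√(2(d² + D²))).

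| D (SD) | At illness | Before, f = 1 | Before, f = 0.5 | Before, f = 0 |
|---|---|---|---|---|
| 0.5 | 0.736 | 0.736 | 0.703 | 0.668 |
| 1.0 | 0.811 | 0.811 | 0.725 | 0.623 |
| 1.5 | 0.882 | 0.882 | 0.760 | 0.592 |

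The arithmetic is sound, but 0.70, D, f and independence are all assumptions. The range begins at no overstatement. The calculation also supposes that at-illness values are used as predictors, which no section says, and that values are recorded equally in both groups, which contradicts the worry that event-free infants have none.

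**6. Is time zero defined?** Not in the supplied text. Two places point to first suspicion: earlier heart rate findings were timed "for 12 to 24 hours and more prior to clinical suspicion", and the third aim seeks metrics "that change in the preclinical phase of sepsis and NEC". With that time zero, tests prompted by suspicion would ordinarily fall after the window closes. With a later time zero, some could fall inside it.

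**The case for a change.** The best case for a change runs as follows. Section 5 is the only statistical section, and the protocol usually lists laboratory data apart from clinical data, so leaving them out there is untidy at least. Choice of predictors and time zero are analysis matters, whereas Section 4 assigns the Manual only data-entry guidance. Laboratory tests come from routine care, so no study schedule keeps tests ordered on suspicion out of the 24-hour window. The rationale asserts that combined data beat any single source, yet no ROC comparison with and without laboratory data is set out. Tightening the wording would cost little, as the results should already be in the record.

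Part of this stands. The wording is inconsistent, and the supplied text gives neither time zero nor a rule for which laboratory values may enter event and event-free windows. Leakage from suspicion-driven tests is therefore an open risk. But an open risk in unstated detail is not a stated rule that leads to a wrong answer. The with-and-without comparison would be a useful addition, but it corrects nothing the plan says.

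**Conclusion.** No change follows. The statements do not contradict one another: the modelling aim supplies the laboratory inputs, Section 5 supplies the window, and the cataloguing aim describes events. Followed in that way, with data available from birth to discharge, the plan yields no demonstrated error.

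What is left is a loose boundary between the terms clinical and laboratory, together with timing detail that analysts building a next-day model would have to settle sensibly: use values available at the moment of prediction, by the same rule with and without an event.

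The size of any bias cannot be derived from the documents. The illustrative ROC areas run from no overstatement to performance below monitor data alone, depending wholly on assumed inputs. The conclusion rests on two assumptions: that Section 5 uses the term clinical as Section 1 does, and that the Manual of Procedures or the analysts fix time zero and laboratory timing. If the Manual showed laboratory entry confined to events, or at-illness values used as predictors, the question would need to be reopened.

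### Section 5 defines neither non-event infant-days nor a maturity benchmark, so a next-day ROC area could largely reflect gestational and postnatal age and would not by itself show early warning

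*Combined protocol and SAP*

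**What the plan says.** The hypothesis in section 2.1 is that combined algorithms "can provide early warning for sepsis and NEC in VLBW infants in the NICU".

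Section 5, Statistical Methods, gives the event window ("The period of interest is the 24 hours prior to the event") and the output ("Thus the output of the model is the probability of an event in the next day"). It then scales that output: "We divide by the average probability of the event, and present the clinician with the fold-increase in risk of an upcoming event". Demographic, clinical and cardiorespiratory variables enter the same model. The ROC area appears under Study Size Considerations and is the only performance measure named.

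The population is broad. Section 3 admits any infant with "Birthweight <1500 grams" and has no exclusions. On follow-up the Synopsis says "Study data are collected from birth until NICU discharge". Section 1 describes the stay as developmental: "Their course of post-natal development in the NICU centers on support of ventilation and nutrition while systems mature". The first primary outcome in the Synopsis is "Late-onset (>3d of age) sepsis"; other late-onset infections are listed next, and NEC is listed with no age cut-off.

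The plan does not say which days serve as the comparison for event days or when at-risk time starts. It describes no matching, stratification or adjustment by GA or postnatal age. It does not say whether postnatal age is a predictor.

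**The concern.** Early warning means that the coming day looks different from other days for a comparable infant. A next-day ROC area taken over whole stays also rewards something else: picking out smaller, younger infants at the ages when these illnesses tend to occur. Bedside staff already know GA and age. Because the stay is a period of maturation, a heart rate, respiratory or saturation metric that only tracks maturity can separate event days from non-event days without carrying any sign of illness.

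At stake is what a good ROC area would mean. The planned validation within and between centers is justified by differences in clinical practice. Maturation happens at every center, so a model driven by maturity could validate well externally. The third aim in section 2.2, finding metrics that alter before illness becomes clinical, is exposed in the same way if its reference period is not comparable in age.

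**Working it through.** The plan states no ROC area, so there is no figure of its own to reproduce here. The question is how large a next-day ROC area can become when risk depends on maturity alone.

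**Inputs from the documents.** 8500 infants (Synopsis); sepsis incidence about 15% (section 5), so 8500 × 0.15 = 1275 events; late-onset sepsis only after day 3 (Synopsis); data from birth to discharge (Synopsis).

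**Assumptions not in the documents.** GA about normal with mean 28 and SD 2.6 weeks, limited to 23–34; discharge near 37 weeks, giving a mean stay of about 63 days; one generic late-onset event; no removal of days after an event. The daily hazard is zero through day 3. After that it is flat, or proportional to d^(k−1)·exp(−d/θ) with θ = peak/(k−1). It is multiplied by r^(28−GA), where r is the factor in risk per week of lower GA, and scaled to 1275 events.

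**Calculation.** The score is the hazard itself, the best score that GA and postnatal age can give. ROC area = P(event-day score > non-event-day score) + ½·P(tie), weighting each infant-day by its event probability h or by 1 − h.

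**Hand check of the simplest case** (flat hazard, r = 1). Only days 0–3 separate from the rest, so ROC area ≈ 0.5 + 0.5 × 4/63 = 0.532. The simulation gives 0.532.

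| Hazard after day 3 | r | All days | After day 3 only | Same postnatal day |
|---|---|---|---|---|
| Flat | 1.0 | 0.532 | 0.500 | 0.500 |
| Flat | 1.5 | 0.754 | 0.738 | 0.720 |
| Peak day 20, k = 2 | 1.0 | 0.628 | 0.602 | 0.500 |
| Peak day 20, k = 2 | 1.5 | 0.759 | 0.743 | 0.735 |
| Peak day 14, k = 2 | 1.0 | 0.689 | 0.668 | 0.500 |
| Peak day 14, k = 2 | 1.5 | 0.790 | 0.776 | 0.744 |
| Peak day 14, k = 3 | 1.0 | 0.758 | 0.742 | 0.500 |
| Peak day 14, k = 3 | 1.5 | 0.841 | 0.830 | 0.748 |

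The range over all days is 0.53 to 0.84. Dropping days 0–3 changes it only to 0.50 to 0.83. Comparing infants on the same postnatal day still leaves up to 0.75, so GA must be handled as well. Within the same GA week and postnatal day the value is 0.50 by construction. A separate simulation with log-normal onset (median day 17 to 25) and 0–35% higher risk per week of lower GA gave 0.67 to 0.81, inside this range.

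**Does comparing predictor sets help?** A pseudo vital sign was defined as postmenstrual age plus noise (SD 2 weeks), with no illness content. Under a day-14 peak:

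| r | GA alone | Marker alone | GA + marker | Gain over GA alone |
|---|---|---|---|---|
| 1.0 | 0.54 | 0.58 | 0.62 | 0.08 |
| 1.25 | 0.58 | 0.64 | 0.66 | 0.08 |
| 1.5 | 0.70 | 0.70 | 0.74 | 0.04 |

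The combination beats each part although the marker knows nothing about illness. With a flat hazard there was no gain over GA alone. Added to a model that already held both GA and postnatal age, the same marker gained 0.00 in every scenario. In the log-normal set, with half-sample testing, adding such a marker to a flexible GA-plus-age model moved the ROC area by at most 0.001 (0.808 to 0.808, 0.780 to 0.780, 0.688 to 0.687, 0.770 to 0.771).

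**The case against.** The strongest reply is that the plan never says all infant-days are pooled. The statement about birth to discharge concerns data collection, and section 5 is silent on control days. This stands: pooling is something a reader might infer, and the accurate finding is that the comparison time is undefined.

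Second, a reader might conclude that the study is unable to show warning at all. The documents do not support that. The Rationale for Study Design in section 1 expects combined data to do better than each type alone, and demographic variables are predictors, so added value over a non-physiologic model could be shown. But section 5 gives no analysis for that comparison, and it protects only if the base model contains postnatal age as well as GA. For the same reason it would be wrong to say that nested comparisons never help because vital signs carry age: with GA and postnatal age in the base model, the artefact disappears.

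Third, the intended product is an absolute risk that deliberately uses demographic information, and an age-matched ROC area as the primary measure would strip that out. This is a fair point. Matching is one option, and the gain over a maturity model answers the question on the plan's own terms.

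Fourth, the third aim can be read as change within an infant, with no pooled comparison intended. That is plausible, but its reference period is not given, and within-infant change over time also contains maturation.

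Finally, the day-3 cut-off should not be extended to NEC, for which the plan states none. The plan also sets no ROC threshold for success, so a false declaration of success is a possibility and not a prediction.

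**Conclusion.** The point holds in a limited form. Section 5 leaves non-event time and a maturity benchmark unspecified. If whole stays are used, the ROC area could largely reflect GA and postnatal age, and would not by itself show warning of imminent sepsis or NEC. With no illness signal, the simulated ROC area is about 0.53 to 0.84. That range rests on an assumed GA spread, discharge age, hazard shape and GA gradient, and on one generic event without separate modelling of NEC. It demonstrates that the problem can arise; it does not estimate its size in this cohort. External validation would not remove an age effect shared by all centers. The gap should be closed because it bears directly on the study's main conclusion and can be closed with data already collected.

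**What to change.** In section 5:

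- Define which infant-days are eligible as non-events, including how days after an event are handled.
- Start at-risk time after day 3 for late-onset sepsis and other late-onset infections. For NEC, state the start of at-risk time explicitly, since the plan gives no age cut-off.
- Base the early-warning conclusion on the gain in ROC area of the full model over a flexible model containing only GA, birthweight and postnatal age.
- Report ROC area within GA and postnatal-age strata as a supporting analysis.
- Identify metrics for the third aim in section 2.2 with the same adjustment for GA and postnatal age.

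The cost is SAP wording and a little more analysis, with no new data. Sparse strata may need wider bands, and the reported gain will look smaller than the overall ROC area.

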6. STUDY MANAGEMENT

Institutional Review Board (IRB) Approval and Consent

This is a purely observational study. Bedside monitor data are currently collected and stored at all sites. Routine clinical data are annotated in the electronic health record. For purposes of this study, waiver of consent is appropriate since there are no interventions, data are considered de-identified under the Privacy Rule since they have only the limited HIPAA identifiers of date and Study ID , (Limited Data Set) and securely stored, and requiring consent would impact the study results since the consented population would be smaller and may differ from the entire VLBW cohort in ways that could impact the validity of the sepsis and NEC algorithms we develop. Data will be collected either prospectively or retrospectively.

7. Study Records and Record Retention

IRB # 21237: Predictive Modeling for Sepsis and Necrotizing Enterocolitis in Preterm Infants

NICHD: RO1 HD072071:

PI: [name],

Version dated March 10, 2025

Study documentation includes all electronic case report forms in REDCap, source documentation, Sponsor-Investigator correspondence, regulatory documents (e.g., protocol and amendments, IRB correspondence and approval) and the like.

Source documentation will be captured in electronic format and include information from patient's electronic medical records and / or data obtained from various bedside vitals monitoring equipment e.g., using BedMasterEx software (Excel Medical), Philips Data Warehouse Connect and include all recordings of observations or notations of clinical activities and all reports and records necessary for the evaluation and reconstruction of the clinical research study.

Study documentation will be kept on file for the length of time that is required by each participating sites IRB.

IRB # 21237: Predictive Modeling for Sepsis and Necrotizing Enterocolitis in Preterm Infants

NICHD: RO1 HD072071:

PI: [name],

Version dated March 10, 2025

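### Does presenting the fold-increase in risk to the clinician turn a data-collection study into one with bedside display?

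*Combined protocol and SAP*

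**What the plan says.** Section 5, Statistical Methods, sets the time frame first: "The period of interest is the 24 hours prior to the event". It continues: "Thus the output of the model is the probability of an event in the next day". That probability is divided by the average event probability, and the team will then "present the clinician with the fold-increase in risk of an upcoming event". The next sentence turns to development and validation cohorts within and between centers, which are meant to allow for differences in practice.

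Elsewhere the study is described as free of intervention. The opening summary says "No interventions are involved". The Synopsis entry for the investigational intervention reads "None (data collection only". Section 6 argues that "waiver of consent is appropriate since there are no interventions", and adds two further grounds: limited identifiers in secure storage, and the selection that a consent requirement would introduce.

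Section 1, Disease Background, says of heart-rate analysis: "The University of Virginia group has reduced one such analysis to clinical practice". It reports abnormal heart rate characteristics "in the heart rates of septic infants for 12 to 24 hours and more prior to clinical suspicion". It also cites a randomized trial in which display alone was followed by a mortality reduction of more than 20%.

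**The concern.** The sentence on the fold-increase is in the present tense and carries no limit to later use. A reader could take it to mean that model output reaches treating staff while data are being collected. On the protocol's own account of the earlier trial, display is not neutral. If it happened, the description of the study as free of intervention would be wrong, and the first ground for the waiver would fail.

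The second worry concerns the data. The lead group has a heart-rate score in clinical use, and the documents do not say whether one was visible at the participating units. A visible score might prompt earlier cultures and treatment. If events are timed at the work-up, the 24-hour window would then start and end earlier and hold fewer abnormal hours. If visibility differed by site, a performance difference between centers would have one more possible explanation.

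**Working it through.** **Wording, read in context.**

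1. The sentences before it in Section 5 are generic: parameters are combined, the output is a probability, the probability is divided by an average. The change to the study's own plan comes in the sentence after it, on cohorts.
2. Section 2.2 (Specific Aims) lists collecting, characterizing, constructing and validating. No aim displays a score.
3. Section 4 (Study Plan) describes REDCap entry from the medical record, stored waveforms with coded timestamps, and file sharing. No step computes a live score. Part of the data is retrospective and cannot have been shown to anyone as output of this study's models.
4. Section 1 (Rationale for Study Design) places the benefit to patients in the future.

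The fold-increase is therefore most naturally the scale on which an eventual tool would report.

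**Effect of the rescaling.** Let p be the predicted probability and m the average event probability. The fold-increase is p/m. If m is one positive constant, p1 > p2 holds exactly when p1/m > p2/m. The ranking and the ROC area do not change, and p is recovered as m × (p/m).

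**Existing score: what the documents' figures can show.** The window is W = 24 h (Section 5). The lead of abnormal heart rate characteristics is L = 12 to 24 h or more (Section 1), so L/W runs from 12/24 = 50% to 24/24 = 100%. Suppose a visible score brought the event time forward by d hours. The documents give no d; 3, 6 and 12 h are assumptions.

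| Assumed d | Share of window replaced, d/24 | Abnormal hours left, L − d, for L = 12 to 24 |
|---|---|---|
| 3 h | 12.5% | 9 to 21 |
| 6 h | 25% | 6 to 18 |
| 12 h | 50% | 0 to 12 |

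These rows follow from the chosen d and are not evidence of a shift. The documents also allow a lead beyond 24 h. Once L is at least 24 + d (30 h for d = 6), the window stays full and the loss is zero. The stated lead concerns septic infants; none is given for NEC. Nothing links lost hours to ROC area or calibration.

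**Direction.** A binormal simulation of 1,000,000 infants took 15% prevalence (the sepsis incidence in Section 5), a simulated ROC area of 0.751 and the top 20% of scores flagged.

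- Removing 10%, 20% or 30% of flagged true events gives 0.737, 0.722 or 0.706.
- Adding event labels to 2%, 5% or 10% of flagged non-events gives 0.755, 0.761 or 0.771.

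The change runs from 0.706 − 0.751 = −0.045 to 0.771 − 0.751 = +0.020. Apart from the prevalence, every input is assumed. The simulation also lets the displayed score be the model under test and uses one record per infant, whereas the plan predicts the next day. It shows that the sign is open, and no more.

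**The case for a change.** The strongest case is that nothing in the documents expressly says that scores are withheld from treating staff, computed offline or shown only after validation. The protocol itself reports that display alone changed mortality, and Section 1 expects analytics to influence decisions on antibiotics. Prospective collection continues: November 2018 plus 10 years runs to November 2028, more than three years after the version of March 10, 2025. A model could be fitted and shown within that time. One clause, and one question to each site, would cost little.

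Two parts of this stand. The sentence has no limiting clause, and the visibility of an existing score is not stated in the documents we have. The rest does not carry over. A score that a unit already uses in routine care is not an intervention of this study, so it does not touch the waiver. Only display of the study's own model could, and the summary, Synopsis and Section 6 all rule out an intervention.

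Asking sites about an existing score would give answers that cannot be interpreted. Visibility would be confounded with center and, where it changed, with calendar time, and some sites could only answer unknown for retrospective data. The planned validation between centers already anticipates practice differences, although it does not name score display or deal with event timing. The Manual of Procedures, which is not among the documents, may say more.

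**Conclusion.** No change follows. The sentence on the fold-increase is loose wording. In context it states an output scale, and under that reading the study's conduct, the waiver rationale and every analysis stay as they are; the numerical effect is zero, given one constant average probability. An author revising the text for other reasons could add a clause, but no result depends on it.

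The question of an existing heart-rate score rests on silence in the documents. A bias would require that a score was visible, that staff acted on it, and that this changed the timing or recording of events. None of the three is documented, and neither the sign nor the size can be derived. The window shifts and the simulated ROC areas are illustrations under assumed inputs and should not be quoted as effects. A descriptive split by display status could not attribute a difference to display, so adding it would bring no gain. The conclusion assumes that the study is run as its summary, Synopsis and Section 6 describe; evidence that model output reached treating staff during data collection would reopen it.
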